Title: Internet-based Mindfulness-based Training (iMBT) for People with Depression: Investigation of its efficacy and mechanism of change

Document date: 24-09-2021

THE CHINESE UNIVERSITY OF HONG KONG

Survey and Behavioural Research Ethics

Application Form

NOTE: This Form is to be completed by researchers whose research studies involve survey or observation on human subjects. Please read the ***Guidelines for Survey and Behavioural Research Ethics*** carefully before completing this Form. Once the Form is completed, please submit together with all relevant documents to the *Survey and Behavioural Research Ethics Faculty Subcommittee* (c/o Faculty Office concerned). With all the necessary information and documents received, the processing time of each application is approximately 6 to 8 weeks from the time of application.

[For SBREC Use Only]	
Reference No.	: _____
Date of Received	: _____
Type of Review	:  Expedited
	 Full

Part A: Basic Information

Project Title

Internet-based Mindfulness-based Training (iMBT) for People with Depression: Investigation of its efficacy and mechanism of change

Name of Grant Applied /Being Applied
(if applicable)

Grant Ref. No. / Account No.
(if applicable)

Name of Principal Investigator
(Please underline the surname)(in full)

[name]

Department / Unit
(in full)

Psychology

[contact]

E-mail Address

[contact]

Name of Supervisor / Course Instructor

For students

Programme and Year of Study

Student ID

Certification of Ethics Training Test(s)

For details, please visit the Research Ethics Training Website (<https://www.research-ethics.cuhk.edu.hk/web/>)

	E-Cert ID	E-Cert End Date
1. Survey and Behavioural Research Ethics	B106610	27/01/2022
2. Publication Ethics	B106610	27/01/2022

Part B: Summary of Research Proposal *(maximum 150 words)*

Summarize, in layperson's language, the objective(s) and significance of the research.

Major depressive disorder is a significant public health concern, and internet-based psychotherapy is a promising therapeutic approach. With growing evidence that mindfulness-based interventions are efficacious in treating depression, this research seeks to examine whether internet-based mindfulness-based therapy (iMBT) is similarly effective. The aims of this study are:

- (1) to evaluate the efficacy of iMBT in treating adults with depression as compared to usual care, and
- (2) to investigate the mechanisms of iMBT with various statistical tools.

If validated, this research can provide support for the clinical utility of iMBT as a stand-alone mental health intervention for people who are clinically depressed. This study will advance our understanding of the causal pathways between mindfulness-based intervention and depression and guide future research, theoretical developments and clinical practice. This effort increases our repertoire of treatment offerings for people with depression.

Part C: Particulars of Research

Human participants

Age range (Check all that apply) 0-17 18-59 60+

Specification of the inclusion and exclusion criteria of the study (if any)

For inclusion, participants must be (1) over 18, (2) have access to computer and mobile phone (since this is an internet-based therapy), and must (3) score >9 on PHQ9, (4) have ability to read and type Chinese. Exclusion criteria includes (1) self-reported presence of psychosis or bipolar disorder, post-traumatic stress disorder, drug or alcohol dependence, current use of antipsychotic medications, (2) self-reported frequent suicidal ideation (more than half of the days in the past two weeks), (3) completion of an online mental health program/research for depression in the past 3 months

1. Does the study use **only** publicly available data? Yes No
2. Does the study involve **only** survey or observation of public officials? Yes No

If you have checked “Yes” to any of the above questions, you can skip Question 3 and go straight to Question 4 to apply for an expedited review.

3. Checklist to determine whether a full review is needed:
 - (a) Does the study involve participants who are unable to give informed consent (e.g. children, individuals with intellectual disabilities or cognitive impairments)? Yes No
(If Yes, please elaborate how consent can be obtained in Question 4.)
 - (b) Will deception of participants be necessary prior to or during the study? *(If Yes, please attach a debriefing form.)* Yes No
 - (c) Details on participant remuneration:
 - (i) Will participants receive inducements or rewards (other than reasonable expenses and compensation for time) before, during, or after participation? Yes No

If Yes, please specify the form of remuneration e.g. cash, course credit, gift certificate. For cash and gift, state the amount; for course credit, state its percentage of the final grade:

Participants can get a maximum of \$200 (either cash or gift certificate) to compensate for time used to complete the assessments.

- (ii) Will the payment be prorated for partial participation? Yes No

- (d) Does the study involve sensitive aspects of the participant's own behaviour such as illegal conduct, illicit drug use, suicidality, and sexual conduct? (If Yes, please provide details in Question 4.) Yes No

- (e) If the observations on the participants are disclosed, will it reasonably place the participant at risk of criminal or civil liability or be damaging to the participant's financial standing, employability, or reputation? Yes No

If Yes, please provide details below:

- (f) Does the study/experiment induce undue psychological stress? Yes No

If Yes, please provide details below:

- (g) Is pain or more than mild discomfort likely to result from participating the study? Yes No

If Yes, please provide details below:

- (h) Does the study involve prolonged and repetitive testing? Yes No

If Yes, please provide details below:

Participants will be expected to complete an Internet-based mindfulness-based training delivered over a 6-week period via an internet e-learning mental health platform. Participants will be assessed at four different time points: (1) before intervention (T0), (2) 2,4 weeks since the commencement of group (T1,2), (3) 6 weeks after (i.e., when the intervention ends) (T3), (4) at 3-month follow-up(T4).

- (i) Will the participants be identified? Yes No

If Yes, please provide details below:

If you have checked "Yes" to any of the above items, you must go through a full review. Please attach a detailed research proposal.

4. Summary of Research Procedures (maximum 300 words)

Describe what the participants will do, where the research activities will take place, the total number of sessions the participants need to participate and their total time commitment. Besides, please attach the instruments (e.g. questionnaire, focus group discussion guide, interview guide, etc.) that will be used in data collection. If the instruments are not yet available, please provide a detailed description of them.

Participants who have provided consent and passed an online screening (based on the above-mentioned inclusion and exclusion criteria) will engage in a 6-week IMBT, consisting of 6 modules with 4 sections each. It is expected that participants will complete one module per week, each module lasting around 1 hour while participants are encouraged to practice for 15 minutes a day. The control group will be advised to seek assistance from their usual healthcare provider when needed.

Both treatment group and control group will be assessed at four different time points: before intervention (T0), (2) 2,4 weeks since the commencement of group (T1,2), (3) 6 weeks after (i.e., when the intervention ends) (T3), (4) at 3-month follow-up(T4).

Initial screening will utilise the PHQ9. Once participants have been recruited, online assessments will be conducted via Qualtrics at each of the aforementioned timepoints. The assessments will include:

- Patient Health Questionnaire (PHQ9)
- Five Facets Mindfulness Questionnaire – Short form (FFMQ-SF)
- Warwick Edinburgh Mental Wellbeing Scale
- Credibility and Expectancy Questionnaire (CEQ)
- Difficulties in Emotional Regulation Scale (DERS)
- Nonattachment scale
- Stillness scale
- Equanimity scale
- Peace of mind scale

5. Will consent form be used? Yes No

If No, please provide reason(s) below:

(a) Type of consent (*Check all that apply*)(Please attach a copy of consent form.)

Formal Consent

- Informed consent
(for participants able to give legal valid informed consent and not belonging to any vulnerable groups)
- Parent/guardian consent
(for participants under 18 years old or those belonging to a vulnerable group)
- Assent form
(for participants not competent to give legal valid informed consent)
- Passive informed consent
(for surveys to be conducted through the schools or other authorities)

Informal Consent

Please provide justifications:

6. Confidentiality of data

(a) Collection of auditory and visual data (*Check all that apply*)

- Audiotapes
- Videotapes
- Still photos
- Not applicable

(b) Does the study involve multi-phase data collection? Yes No

If Yes, please explain the tracking and coding system(s):

Participants will be identified by a unique ID to match their data across time.

- (c) Does the study involve collecting data through an Internet survey platform? Yes No

If Yes, please address the confidentiality of data collected via e-mail, Web interfaces, and other networked information:

Major depressive disorder is a significant public health concern due to its high prevalence, high disease burden, and common comorbidity. One promising approach to enhance the accessibility and serviceability of psychotherapy is to complement the existing health system through evidence-based self-management programs delivered via the Internet. Despite the growing evidence of the efficacy of mindfulness-based interventions in the treatment of an array of physical health and mental health conditions, research into the efficacy of Internet-based mindfulness programs and its therapeutic mechanism on the treatment of common mental disorders is relatively scarce. Through the development of Internet-based mindfulness-based training (iMBT) and close examination of its mechanisms, detailed refinement in the program development can be made to maximize its effectiveness for specific populations.

With reference to the current research and service gap, our aims of this study are:

- (1) to evaluate the efficacy of iMBT in treating adults with depression as compared to usual care, and
- (2) to investigate the mechanisms of iMBT using latent growth curve modelling

We expect that the newly developed iMBT will have favorable effect on depressive symptoms, mindfulness, difficulties in emotion regulation, and positive mental well-being among adults with depression.

Long-term Significance

Practically, given the popularity of mindfulness and wide-spread adoption of e-therapy, this research can provide support for the clinical utility of iMBT as a stand-alone mental health intervention for people who are clinically depressed. Theoretically, this study will advance our understanding of the causal pathways between mindfulness-based intervention and depression and guide future research, theoretical developments and clinical practice. This effort increases our repertoire of treatment offerings for people with depression. Especially, in light of the long waiting time in the public mental health services, the expansion of evidence-based online interventions provide an effective and efficient way for individuals with varied mental health needs to obtain the interventions they need. By systematically testing iMBT as a possible treatment of choice for people with depression, we add to the offerings of Internet-based interventions as expand the use of iMBT to not only for mental health promotion and mental illness prevention, but also treatment for depression.

In addition to establishing its effectiveness in the treatment of depression, by dismantling the process by which iMBT lead to changes in individuals' approach to life and subsequent improvement in their mental well-being, we can further deliberate how to adapt iMBT to increase awareness and maximize gains. This proposal is one of the series of attempts in my research lab that aims to build a wide repertoire of online programs and services with the aims to improve public mental health. The building of a versatile iMBT portal in this application through Learning Management System would allow our team to continue to conduct research on online interventions with the aims to develop personalized public mental health.

How will this proposal be developed into RGC General Research Fund (GRF) / Early Career Scheme (ECS) proposal? (*A maximum of one A4 page*)

If iMBT is showed to be effective in the treatment of people with depression, our next step is to conduct a non-inferiority trial comparing iMBT with Internet-based cognitive behavioral therapy (iCBT) in the treatment of common mental disorders. The reason for this progression being iCBT is a well-established intervention for the treatment of depression and anxiety. A recent meta-analytic review showed that iCBT was as effective as its face-to-face counterpart for clinical practice in treating depression¹⁶. If iMBT is demonstrated to be as effective as iCBT in the non-inferiority trial, we have the potential to increase our repertoire of mental health services and approaches to the general public for the treatment of common mental disorders. So far, no study has compared these two streams of intervention approaches, especially online interventions. Moreover, with this step, we will be in greater position to identify moderators that help us determine which interventions are suitable for whom under what kind of circumstances. This question is essential in the development of personalized mental health care.

In subsequent grant proposal, we aim to further dissect and unpack the active ingredients in iMBT and iCBT that allows us to make more precise prediction for individuals' outcomes. With more data being collected, we also aim to leverage machine learning and big data analytics to observe patterns that allow us to refine our approaches for based on individuals' psychosocial profiles. Under implementation science, our aim is to understand how best to implement different online and low-intensity approaches by investigating on usage patterns, adherence factors, specific features of each program, and match between person's preferences with program's offerings.

5. Background of Research (*A maximum of three A4 pages, including references.*)

Summary of related work already done by you and other researchers, and outline of previous and alternative approaches to the issue:

1.1 Internet delivered Intervention for Depression

Major depressive disorder (MDD) is a significant and common public health concern due to its high prevalence, high disease burden, and common comorbidity¹⁻³. While evidence-based psychological treatments are available, most of those affected by depression do not have access to these treatments or seek help⁵. Several reasons such as long waiting time of mental health service, barriers in access to care, and reluctance to seek help due to stigma are contributing to this situation⁶. One promising approach to enhance the accessibility and serviceability of psychotherapy is to complement the existing system using evidence-based self-management programs delivered via the Internet. Different forms of psychotherapy, could potentially be transferable to Internet-based interventions, especially when guided by coaches⁹ who provide online guidance, encouragement, and therapeutic activities^{10,11}. The initiatives of translating and scaling up mental health service via the Internet echo with the National Institute for Health and Care Excellence guidelines (NICE) for managing depression¹². The guideline recommended low-intensity Internet-based interventions as first line treatment prior to more complex higher-tier services. Internet-based interventions for major depression has not only been shown to be efficacious¹³, but also cost-effective and able to generate societal savings^{14,15}. Notably, a recent meta-analytic review revealed that Internet-based cognitive behavioral therapy (iCBT) was as effective as its face-to-face counterpart for clinical practice in treating depression¹⁶. Given the high accessibility and low recurring costs of Internet-based interventions for depression, these interventions are suggested to have a huge potential for public mental health impact.

1.2 Mindfulness-based Training as an Internet delivered Intervention for People with Depression

In addition to iCBT, Internet-based mindfulness-based training (iMBT) has also gained evidence in improving mental well-being and reducing psychological distress. Mindfulness is defined “paying attention in a particular way: on purpose, in the present moment, and nonjudgmentally”^{17,18}. In the context of understanding the beneficial effect of mindfulness on depression, it is theorized that mindfulness training reduced depression through encouraging individuals to notice experiences regardless of its valence labelled, and to approach those experiences with gentleness, curiosity and interest without suppressing, judging, or pushing these experiences away¹⁹. In turn, repetitive negative thinking, which involves cognitive over-engagement in attempt to control unpleasant inner experiences, would be attenuated by the facilitation of individuals’ processing of their affective experiences^{17,20}. Moreover, through observing that different experiences come and go over time, mindfulness practitioners come to know the impermanent and transitory nature of the inner experience and realize that it is not always necessary to react.

A recent meta-analysis that included 209 studies with 12,145 participants concluded that mindfulness-based intervention is an effective treatment for various psychological problems, and is especially effective for reducing depression, anxiety and stress²¹. Evidence of online mindfulness-based intervention has demonstrated its effectiveness among community samples and subclinical populations with elevated depressive symptoms^{23,24}. In addition, iMBT may be more acceptable than intervention using the traditional cognitive behavioral approach. As reported in a recent study, intervention with mindfulness element was chosen as the first option of intervention by over 80% of people with depression/anxiety. Moreover, nearly half of the participants in a study reported preference of online formats for mindfulness interventions over group/individual formats²⁸.

Given its acceptability and preference by individuals with mental health needs and its promising effects in reducing depressive and anxiety symptoms, another critical question lies in examining how MBT works so that further refinement of such approach can be made based on its theoretical roots and mechanism of change. The precise mechanisms underlying the effect of mindfulness have received recent theoretical attention^{19,29,30}. Despite not having abundant studies, recent meta-analysis of mediation studies with 12 RCTs identified consistent evidence for the change in mindfulness as a mechanism underlying MBIs³¹. However, simply identifying mindfulness as the mechanism of change in MBT is too crude and intuitive. Further unpacking the effects of mindfulness is necessary to understand the process through which individuals experience changes. One possibility is to examine specific effect of each facet in mindfulness (i.e., observe, describe, act with awareness, non-react and non-judgement). Correlational study suggested that different facets of mindfulness have differential relationships with various psychological variables³². Although most facets of mindfulness are frequently found to be associated with reduced psychological distress, the “observe” facets is often uncorrelated or even positively correlated with mood symptoms³³. In accord with the Acceptance and Monitor theory¹⁹, a recent study showed high observing skills was correlated with higher depressive symptoms with low acceptance. Yet, high observing skills in combination with high acceptance correlated with increased adaptive cognitive processing tendencies³⁴. Consequently, it is important to examine relationships between change of mindfulness and that of psychological symptoms at the facet level to provide a more fine-grained perspective on the contribution of mindfulness. This could also facilitate refinement of iMBT.

1.3 Aims and hypotheses

The research goals of this randomized controlled trial are to determine the feasibility and the mechanism of change of iMBT that has been developed using the Acceptance Checklist for Clinical Effectiveness Pilot Trials (ACCEPT) framework³⁵.

The primary research question is as follows:

- What is the effectiveness of the iMBT in relation to improvements on depressive symptoms among people with clinical depression, relative to a usual care control after the intervention and in 3-month follow-up?

Secondary questions include the following:

- Which facet(s) of mindfulness (i.e., observe, describe, act with awareness, non-react and non-judgement) improved during the intervention?
- How does the growth trajectory of different facets of mindfulness relate to the improvement of well-being and reduction of ill-being?

We hypothesize that:

- H1 Participants in iMBT group will have greater reduction in depressive symptoms and increase in all facets of mindfulness and mental well-being, than the usual care group at post-intervention, and 3-month follow-up.
- H2 Using latent growth analysis, the intraindividual growth trajectory of the monitor and acceptance facets of mindfulness would mediate the effect of iMBT on the intraindividual changes in depressive symptoms.
- H3 Using multi-group analysis, in accord with Acceptance and Monitor theory, the relationship between the growth trajectory of monitor facets of mindfulness and the growth trajectory of depressive symptoms will be moderated by the level of acceptance. People with greater acceptance of inner experience will benefit more from the change of monitor facets of mindfulness in iMBT.

References

1. FerrariAJ, SomervilleAJ, BaxterAJ, et al. Global variation in the prevalence and incidence of major depressive disorder: A systematic review of the epidemiological literature. *Psychol Med*. 2013. doi:10.1017/S0033291712001511
2. LiuQ, HeH, YangJ, FengX, ZhaoF, LyuJ. Changes in the global burden of depression from 1990 to 2017: Findings from the Global Burden of Disease study. *J Psychiatr Res*. 2019. doi:10.1016/j.jpsychires.2019.08.002
3. PatelV, ChisholmD, ParikhR, et al. Addressing the burden of mental, neurological, and substance use disorders: Key messages from Disease Control Priorities, 3rd edition. *Lancet*. 2016. doi:10.1016/S0140-6736(15)00390-6

2.1 Trial design, Procedure and Study Flow

A two-armed parallel RCT following CONSORT statement¹ will be conducted to examine the efficacy of an Internet-based mindfulness-based training (iMBT) to a treatment-as-usual control group (TAU). Intervention (iMBT) will be delivered over a 6-week period via an internet e-learning mental health platform.

All participants who are interested to join this research will be provided with an electronic informed consent form, and online screening. The online screening included a self-assessment of depressive symptoms using PHQ-9 as well as items that assessed the inclusion and exclusion criteria.

Participants will be included if they are: (1) aged over 18, (2) have access to computer and mobile phone, (3) scored > 9 on PHQ-9, administered via telephone by trained interviewers, and (4) have ability to read and type Chinese. Exclusion criteria includes (1) self-reported presence of psychosis or bipolar disorder, post-traumatic stress disorder, drug or alcohol dependence, current use of antipsychotic medications, (2) self-reported frequent suicidal ideation (more than half of the days in the past two weeks), (3) completion of an online mental health program/research for depression in the past 3 months.

Any excluded applicants will receive contact information on community mental health services. Following telephone assessment, eligible participants will be randomized to either iMBT or TAU by block randomization with block number of 6 with allocation ratio of 1:1.

Participants will be assessed at the following time points: (1) before intervention (T0), (2) 2,4 weeks since the commencement of group (T1,2), (3) 6 weeks after (i.e., when the intervention ends) (T3), (4) at 3-month follow-up (T4). Participants in the TAU will have the assessment according to specific times as the iMBT group (i.e. weeks since commencement of group) (see Figure 1).

[figure not shown]

Figure 1 CONSORT flow diagram

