2.2.2 Treatment-as-usual control group (TAU)

The TAU group will be advised to seek assistance from their usual healthcare provider when needed.

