2.3 Power Calculation and Sample Size

Based on past research⁵, we expected a small to medium ($f = 0.11$) difference between the iMBT and the TAU control group. Thus, using G * Power software (version 3.1.9.2), a sample size of 116 will be needed to detect superiority of the intervention groups over the TAU control group with 80% power.

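### A single stated block size of 6 in a trial that cannot be masked would make up to a quarter of allocations certain to a recruiter who knows the block size and the earlier allocations

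*Protocol*

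**What the plan says.** Section 2.1 describes the design as "A two-armed parallel RCT following CONSORT statement". It gives one block figure, with no variation in size and no stratification: allocation is "by block randomization with block number of 6 with allocation ratio of 1:1".

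The same section sets the order of events: "Following telephone assessment, eligible participants will be randomized to either iMBT or TAU". One entry criterion is that the person "scored > 9 on PHQ-9, administered via telephone by trained interviewers". The psychiatric and suicidality exclusions are self-reported. Item 4 of Part C (Summary of Research Procedures) describes entry differently and mentions no interviewer: "Participants who have provided consent and passed an online screening".

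Section 2.2.1 gives the intervention arm six online modules with weekly written feedback from a coach. For the control arm, section 2.2.2 says: "The TAU group will be advised to seek assistance from their usual healthcare provider when needed". Section 2.3 sets the size: "a sample size of 116 will be needed to detect superiority of the intervention groups over the TAU control group with 80% power".

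The text does not say who generates or holds the sequence, who assigns participants, or whether interviewers see earlier allocations or the block size.

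**The concern.** Permuted blocks of one known size are predictable towards the end of each block. Once three people in a block of six have gone to one arm, everyone left in that block must go to the other. In a masked trial this matters little, because past allocations stay hidden. Here an allocation is plain to the participant and to the coach, so past allocations could become known to staff unless the procedure prevents it.

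Randomisation also comes straight after a step carried out by a person. An interviewer who expected a particular arm could affect who enters through prompting, the handling of a borderline score, or the timing of a call. If that happened, the arms could differ in prognosis in ways the analysis cannot fully correct. The planned difference is modest (section 2.3: "we expected a small to medium ($f = 0.11$) difference between the iMBT and the TAU control group"), which leaves little room for even a small bias.

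**Working it through.** The protocol gives no predictability figure, so there is none to reproduce.

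**Inputs**
- Block size 6, ratio 1:1, two arms: three and three per block (section 2.1; 6 is read as a size).
- 116 participants (section 2.3): 116 = 19 × 6 + 2, that is 19 full blocks and 2 further allocations.
- Assumption: the observer knows the block size and every earlier allocation in order. The protocol neither states nor excludes this.

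**Forced allocations, fixed size**
- For a block of 2m, the expected number of allocations made after one arm is used up is 2m/(m + 1), a share of 1/(m + 1).
- With m = 3: 6/4 = 1.5 per block, or 25%.
- Check by listing all C(6,3) = 20 orders: one forced allocation in 60% of blocks, two in 30%, three in 10%. 0.6 × 1 + 0.3 × 2 + 0.1 × 3 = 1.5.
- Over the trial: 19 × 1.5 = 28.5, and 28.5/116 = 24.6%. The last two allocations start a new block and cannot be forced.

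**Best-guess success, fixed size**
- Always guessing the arm with more places left gives [m + (2^(2m)/C(2m,m) − 1)/2]/(2m).
- With m = 3: 64/20 = 3.2; (3.2 − 1)/2 = 1.1; (3 + 1.1)/6 = 68.3%. Over 116 participants it is 68.1%. Chance is 50%.

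**Randomly varying sizes**

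These come from simulated lists of 116. The observer knows the set of possible sizes and all past allocations, but not the order of the sizes.

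| Scheme | Certain | Best guess correct |
|---|---|---|
| Fixed 6 | 24.6% | 68.1% |
| Random 6, 8, 10 | about 1.6% | about 66% |
| Random 4, 6, 8 | about 2.2% | about 68% |
| Random 4, 6 | about 5.5% | about 69% |
| Random 2, 4, 6 | about 4.2% | about 70% |
| Any size, past allocations hidden | 0% | 50% |

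Separate runs for 6, 8 and 10 ranged from 1.4% to 1.8% certain. At 1.6%, that is 0.016 × 116 = about 2 allocations, against 28.5.

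**The other reading of the wording**

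If 6 were the number of blocks, each would hold 116/6 = 19.3, or about 20. Then m = 10 and the forced share is 1/11 = 9.1%.

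**The case against.** The strongest reply is that predictability is not bias. The quarter applies only to someone who has both the block size and the full ordered list of past allocations, and nothing says the interviewers have either. Figure 1 and parts of the form were not in the text available, so a concealment statement there cannot be excluded. This stands, and it is why the figure is given as an upper limit.

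Three stronger readings are tempting, and the documents do not support them:
- A reader might infer that one laboratory screens, allocates and coaches, so that interviewers must know past allocations. No section says so. Section 2.1 mentions trained interviewers and section 2.2.1 a student coach; neither says who allocates.
- A reader might infer that an altered eligibility score passes directly into the outcome, because both use the PHQ-9. Item 4 of Part C has the assessments after recruitment, T0 included, completed online. The model in section 2.4.1 has time, group and their interaction, so a difference in severity at T0 would be visible and partly absorbed. Bias through unmeasured prognosis remains possible, but the route is indirect.
- A reader might infer wide interviewer discretion. The cut-off is numeric, the exclusions are self-reported, and section 2.1 also has an online self-assessment.

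It can also be said that varying the sizes hardly helps, because guessing stays near two in three. That is right about guessing, and sets with smaller blocks can even make it worse. Much of the small gain with 6, 8 and 10 comes from the larger blocks: the size-weighted mean for fixed 6, 8 and 10 is (6 × 68.3 + 8 × 66.6 + 10 × 65.3)/24 = 66.5%. It is not right about certainty, which falls more than tenfold.

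**Conclusion.** The point holds as a cheap improvement to a stated design choice. It does not show that the trial is biased. Section 2.1 states a single block figure, worded so that it can be misread, in a trial whose arms cannot be masked and just after an interviewer-led eligibility step.

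The exposure lies between 0% of allocations (full concealment) and 24.6% (a fully informed recruiter). It rests on reading 6 as a fixed block size; on the other reading the upper limit is 9.1%. No effect on the PHQ-9 contrast has been estimated, and none can be from the protocol. Varying the block size removes most of the certainty but little of the guessability, so the main protection is hiding the sequence and past allocations from whoever judges eligibility.

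**What to change.** In section 2.1:
1. Say block size where that is meant.
2. Replace the single size with permuted blocks whose sizes vary at random, for example 6, 8 and 10, and keep the sizes out of any document that recruiters see.
3. State that each allocation is released by computer only after the eligibility result and the T0 assessment are recorded, and that the sequence and earlier allocations are hidden from the interviewers. If this is already the practice, one sentence saying so is enough.
4. Reconcile the online and telephone descriptions of screening in Part C item 4 and section 2.1.

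The cost is a few sentences and a new randomisation list, with no extra participants. The downside is a slightly larger possible imbalance if recruitment stops inside a block: at most half the largest block, so 5 instead of 3.
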